9.2. Adverse Events

An adverse event (AE) is defined as any untoward medical occurrence associated with the use of the investigational product in humans, whether or not considered related to investigational product. An AE (also referred to as an adverse experience) can be any unfavorable and unintended sign (eg, an abnormal laboratory finding), symptom, or disease temporally associated with any use of the investigational product, without any judgment about causality and irrespective of route of administration, formulation, or dose, including an overdose.

AEs include, but are not limited to: (1) a worsening or change in nature, severity, or frequency of condition(s) present at the start of the study; (2) subject deterioration due to primary illness; (3) intercurrent illness; and (4) drug interaction. For reporting purposes, pregnancy is not considered an AE.

For subjects who enrolled into the study, AEs will be mapped to PTs and SOCs using MedDRA dictionary version 23.1 (or later version). Subjects experiencing the same event more than once will be counted only once at the most severe grade and the closest relationship to study treatment.

9.2.1. Treatment-Emergent Adverse Events

A TEAE is any event not present prior to the initiation of the IP or any event already present that worsens in either intensity or frequency following exposure to the IP or within 30 days after the discontinuation of the study treatment.

9.2.2. Serious Adverse Events (SAE)

An AE is considered “serious” if, in the view of either the Investigator or Sponsor, it results in any of the following outcomes:

- Death
- Is immediately life threatening
- Requires in-subject hospitalization or prolongation of existing hospitalization
- Results in persistent or significant disability or incapacity
- Results in a congenital abnormality or birth defect
- Is an important medical event that may jeopardize the subject or may require medical intervention to prevent one of the outcomes listed above

Events not considered to be SAEs are hospitalizations for:

- Routine monitoring of the studied indication and not associated with any deterioration in condition or AE
- Elective treatment for a pre-existing condition that did not worsen

- Respite care or observation when there is no AE associated with the hospitalization

9.2.3. Adverse Events of Special Interest (AESI)

The following decompensation events are adverse events of special interest:

- Hepatic decompensation/disorder events
 - Hepatic Disorders SMQ, excluding the following sub-SMQs:
 - Alcohol related
 - Congenital, familial, neonatal, and genetic disorders of the liver
 - Liver infections
 - Pregnancy-related hepatic disorders
- Cholecystitis/Cholelithiasis
 - Defined by Gallbladder related disorders narrow SMQ and Gallstone related disorders narrow SMQ
- Renal
 - Defined as events included in the following broad SMQs: acute renal failure, chronic kidney disease, proteinuria, renovascular disorders, or tubulointerstitial diseases
- Cardiovascular
 - Defined by the embolic and thrombotic events broad SMQ, ischaemic heart disease broad SMQ, or central nervous system vascular disorders narrow SMQ.
 - These events may be reassessed stratified by statin (or other lipid lowering medication) usage
- Dyslipidemia
 - Defined by the Dyslipidemia SMQ
 - These events may be reassessed stratified by statin (or other lipid lowering medication) usage
- Pruritus
 - Defined as any preferred term within the Pruritus Not Elsewhere Classified (NEC) high level term or any preferred term including “prur”

9.2.4. TEAE Analyses

The number of events and counts and percentages of unique subjects experiencing a TEAE and TEAEs by PTs and SOC in the following categories will be presented for the Safety Population:

- TEAEs

- TEAEs by highest severity (mild, moderate, severe): At each level of subject summarization, a subject is classified according to the highest severity if the subject reported 1 or more events. AEs with missing severity will be considered severe for this summary.
- Serious AEs
- Adverse events of special interest
- AESIs by highest severity (mild, moderate, severe): At each level of subject summarization, a subject is classified according to the highest severity if the subject reported 1 or more events. AEs with missing severity will be considered severe for this summary.
- TEAEs leading to study treatment discontinuation: This is a subset of the AEs where action taken with study treatment is checked as “Drug withdrawn” or where “Subject Discontinued from Study” is checked.
- TEAEs leading to study treatment interruption: This is a subset of the AEs where action taken with study treatment is checked as “Drug interrupted”.
- TEAEs leading to study treatment dose reduction: This is a subset of the AEs where action taken with study treatment is checked as “Dose reduced”.
- Deaths: This is a subset of the AEs where “Fatal” is checked.
- Subject incidence of TEAEs by MedDRA SOC, PT, and closest relationship to investigational product (Related/Not Related). Related AEs are those with relationships reported by the Investigator as “Definite,” “Probable,” or “Possible,” and unrelated AEs are those with relationships reported as “Unlikely” or “Not Related.” At each level of subject summarization, a subject is classified according to the closest relationship if the subject reported 1 or more events. AEs with a missing relationship will be considered related for this summary.

Summaries will be sorted in order of decreasing frequency in the treatment arm. Summaries will also be presented by MedDRA SOC and PT, sorted in alphabetic order of SOC and then in order of decreasing frequency in the treatment arm.

Exposure-adjusted incidence of TEAEs will also be provided by SOC and PT. Each individual subject year on study will be derived as the last known date during the study minus the first dose date plus 1 divided by 365.25 days/year.

Exposure-adjusted incidence rates will additionally be provided by SOC and PT for “on-risk” AEs. An on-risk adverse event (ORAE) is any event not present prior to the initiation of the IP or any event already present that worsens in either intensity or frequency following exposure to the IP or within 30 days after the discontinuation of the regularly-scheduled study visits. As some subjects may be on commercial OCALIVA after discontinuing study treatment and prior to discontinuing regularly scheduled study visits, ORAE events will be summarized prior to initiation of commercial OCALIVA.

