	Standard	Modified
	Noncirrhotic/ Child-Pugh A	Child-Pugh B or Child-Pugh C
Starting Dose ^a (Day 0)	5 mg daily	5 mg once weekly
Titration 1 ^b (≥Month 3)	10 mg daily	5 mg twice weekly
Titration 2 ^b (≥6 weeks after Titration 1)	NA	10 mg twice weekly

^a Starting dose based on subject's cirrhosis status and Child-Pugh Score at Screening.

^b Planned titration regimen is shown; however, the titration of dose and/or frequency is dependent on subject tolerability, biochemical response, and/or changes in cirrhosis status or Child-Pugh Score at any time during the study

^c Dosing per the twice weekly schedule must be at least 3 days apart.

With the exception of liver transplant, if a subject experiences a suspected or confirmed clinical outcomes event, the subject should continue the regular visit schedule and continue taking IP as long as the subject has not met any of the criteria for discontinuation outlined in the protocol. Subjects who discontinue IP are expected to be followed through to study closure (or at the discretion of the Sponsor).

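### Section 9.2.4 uses whole time on study as subject-years with no stop at the first event; read with the once-only counting rule in 9.2, this understates first-event rates for frequent adverse event terms

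*SAP*

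**What the plan says.** - **Measure (SAP 9.2.4).** "Exposure-adjusted incidence of TEAEs will also be provided by SOC and PT". The numerator of this measure is not written out.
- **Denominator (9.2.4).** "Each individual subject year on study will be derived as the last known date during the study minus the first dose date plus 1". The day count is then converted to years. This gives one length per person, whatever the term and whether or not the event has occurred.
- **Counting rule (9.2).** "Subjects experiencing the same event more than once will be counted only once"; the sentence then says which grade and relationship to keep.
- **Contents of the TEAE tables (9.2.4).** "The number of events and counts and percentages of unique subjects experiencing a TEAE", so event counts and subject counts both appear.
- **On-risk rates (9.2.4).** "Exposure-adjusted incidence rates will additionally be provided by SOC and PT" for a wider event window that is cut at commercial OCALIVA. No separate denominator is given.
- **Subgroups (9.8).** The exposure-adjusted incidence is repeated by baseline disease stage, again with no separate denominator.
- **Event window and follow-up.** A TEAE must arise on treatment or "within 30 days after the discontinuation of the study treatment" (9.2.1). Section 9 drops data after commercial OCALIVA. Section 3 adds: "Subjects who discontinue IP are expected to be followed through to study closure".

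**The concern.** If a subject counts once per term, that subject cannot add to the numerator after the first event. The 9.2.4 formula still credits all the later time to the denominator. The rate then falls below the rate of first events, and the gap widens as a term becomes more common and as its events come earlier. If the term is more frequent on OCA, the understatement tends to be larger in that arm, so an informal comparison of the arms would look milder than the first-event rates would show. Within an arm, every row becomes the crude percentage divided by the same mean follow-up, so the table adds no adjustment for time at risk that is specific to the term.

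**Working it through.** The SAP states no adverse event rate, so there is no figure to reproduce. The check is person-time arithmetic.

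**Inputs.** The denominator rule is from 9.2.4 and the once-only numerator is read from 9.2. Assumed: the proportion p with the event, the event timing, follow-up T = 4 years, and equal follow-up in the arms unless stated. Section 3 expects a minimum of about 6 years.

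**Step 1: direction.** The rate as written is subjects with the event divided by total time. The first-event rate is the same numerator divided by time up to the first event. No subject's time to first event exceeds that subject's total time, so the rate as written can never be the higher one. The shortfall s is the share of total time that falls after first events.

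**Step 2: size under a constant hazard.** The first-event rate is λ = −ln(1−p)/T and the rate as written is p/T, so s = 1 − p/(−ln(1−p)). T cancels.

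- p = 10%: 1 − 0.10/0.105 = 5%
- p = 30%: 1 − 0.30/0.357 = 16%
- p = 50%: 1 − 0.50/0.693 = 28%
- p = 70%: 1 − 0.70/1.204 = 42%

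**Step 3: arm ratio with equal follow-up.** The ratio as written equals the first-event ratio × (1 − s for OCA)/(1 − s for placebo). Rates are per 100 person-years at T = 4.

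| OCA vs placebo, p | As written | Ratio | First event | Ratio |
|---|---|---|---|---|
| 10% vs 5% | 2.5 vs 1.25 | 2.00 | 2.6 vs 1.3 | 2.05 |
| 50% vs 30% | 12.5 vs 7.5 | 1.67 | 17.3 vs 8.9 | 1.94 |
| 70% vs 50% | 17.5 vs 12.5 | 1.40 | 30.1 vs 17.3 | 1.74 |

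Check on the last row: 1.74 × 0.58/0.72 = 1.40. At T = 6 the ratios are unchanged.

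**Step 4: early events.** Put the mean first event at 0.25 year, with 70% vs 50%. Mean time at risk is 0.7 × 0.25 + 0.3 × 4 = 1.375 years on OCA and 0.5 × 0.25 + 0.5 × 4 = 2.125 years on placebo. First-event rates are 0.70/1.375 = 50.9 and 0.50/2.125 = 23.5 per 100 person-years, ratio 2.16. As written the ratio is still 1.40. The OCA shortfall is 1 − 1.375/4 = 66%.

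**Step 5: unequal follow-up.** Keep Step 4, but let a share q of OCA subjects with the event leave the study at the event, and no placebo subjects. The first-event ratio stays 2.16. The ratio as written becomes:

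- q = 0: 1.40
- q = 25%: 1.67
- q = 50%: 2.08
- q = 75%: 2.76
- q = 100%: 4.07

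The ratio therefore shrinks only when time after the event is a larger share of total time on OCA than on placebo.

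**Step 6: end of the window.** TEAEs stop counting 30 days after treatment ends and at commercial OCALIVA, while the 9.2.4 time runs to the last known date on study. Time in which no TEAE can count therefore also enters the denominator. This is a related fault in the same formula. It is not quantified here, and correcting it alone would not stop time at the first event.

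**The case against.** The strongest objection is that 9.2.4 never says the numerator is subjects. Its tables also show event counts, and the once-only sentence in 9.2 goes on to grade and relationship, so it could be meant only for those tables. If all occurrences are counted, time after the first event belongs in the denominator and only the window mismatch remains. This stands as a limit: the subject numerator is inferred. Still, the rule sits in the general adverse event section and the measure is called incidence, so subjects are the natural reading. On either reading the numerator needs to be stated.

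A reader might also infer more than the document supports:

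- **That the arm ratio always shrinks.** Step 5 shows that it can grow. Section 3 expects follow-up after treatment stops, which makes shrinkage plausible. Section 14.1 reports high discontinuation rates, so similar follow-up cannot be taken for granted.
- **That pruritus rates in particular are badly understated.** Section 9.2.3 lists pruritus as an event of special interest but gives no frequency or timing. It is also a grouped definition, whereas these rates are by SOC and PT.
- **That the table makes no adjustment for follow-up.** Dividing by total time does adjust for arms followed for different lengths. It does not remove time after the event.
- **That the on-risk rates explicitly use the same formula.** No denominator is written for them; carrying the formula over is an inference.

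Finally, section 9 plans no inferential comparison of safety endpoints unless otherwise specified, and none is specified for these rates. They stand beside event counts and crude percentages. That limits the consequences but does not correct the rate.

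**Conclusion.** The point holds on the joint reading of 9.2 and 9.2.4: subjects counted once, divided by whole time on study, understate the first-event rate. That direction needs no hazard assumption. The size does: with a constant hazard and equal follow-up the shortfall is negligible for rare terms (about 5% at 10% incidence) and substantial for frequent ones (about 28% at 50%, 42% at 70%); early events make it larger. Movement of the OCA-to-placebo ratio toward 1 is the expected direction with similar follow-up, not a certainty. The incidences, timing and departure shares are illustrations, not trial data. The affected tables are descriptive, so no formal test is compromised.

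**What to change.** In 9.2.4, and for the on-risk rates and 9.8, define the exposure-adjusted incidence rate as the number of subjects with at least one event of the term, divided by the sum of years from first dose to the first event of that term or, if none, to the end of the window in which events are counted. State that end:

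- **TEAEs:** the earliest of last IP dose + 30 days, start of commercial OCALIVA, and last contact.
- **On-risk events:** the earliest of last regularly scheduled visit + 30 days, start of commercial OCALIVA, and last contact.

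If an event rate is also wanted, count all occurrences over that full window and label it as an event rate.

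The cost is SAP wording and a person-time derivation for each term in the adverse event program, with no new data. The drawback is that the denominator differs by term and must be displayed on every row.

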9. SAFETY ANALYSES

Safety analyses include exposure to study treatment, treatment-emergent adverse events (TEAEs), clinical laboratory parameters, electrocardiograms (ECGs), vital signs, and any abnormal findings observed during physical examinations after study enrollment and through discontinuation of study treatment or within 30 days after the discontinuation of study treatment. Data after a patient begins commercial OCALIVA will be excluded. Safety analyses will be performed using the Safety Population including by treatment groups. No inferential comparison of safety endpoints will be performed, unless otherwise specified.

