9.3. Adjudicated Cardiovascular Events

Major Adverse Cardiovascular Events (MACE) (defined as death, myocardial infarction, and stroke) are included in the Cardiovascular Adjudication Committee Charter for adjudication. The adjudication of these events will be handled separately from the adjudication of events for assessment of the primary clinical composite outcome endpoint in this study.

Adjudicated MACE is a time-to-event endpoint and will be summarized for the Safety Population.

OCA and placebo treatment groups will be compared using the log-rank test stratified by the randomization stratification factors. In addition, the hazard ratio and 95% CI will be determined based on a Cox regression model stratified by randomization strata to estimate the magnitude of the effect.

The number and percent of subjects censored and with events will be presented. Descriptive statistics will be presented for the time-to-event.

Kaplan-Meier (KM) estimates of the distribution of the time-to-event will be tabulated and graphed by treatment group. The tabulation will include the KM estimate of the 25th, 50th (median), and 75th percentiles and corresponding 95% CIs, where the percentiles can be estimated. KM tabulations will present time to event in days; KM graphs will present time to event in months. The hazard ratio and 95% CI will be estimated based on a Cox regression model stratified by randomization strata.

Only adjudicated events will be included in analyses. Subjects without any documentation of events will be censored at the date of last contact. For subjects with more than one event, the earliest of the event dates will be used.

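### Exposure-adjusted TEAE rates count events from an on-drug window but divide by all time on study, which understates the rates and distorts the arm comparison if off-drug time differs between arms

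*SAP*

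**What the plan says.** **Event window.** Section 9.2.1 counts an event as treatment-emergent if it starts or worsens on IP or "within 30 days after the discontinuation of the study treatment". The opening of Section 9 gives the same limit for safety data, "within 30 days after the discontinuation of study treatment", and adds: "Data after a patient begins commercial OCALIVA will be excluded".

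**Person-time.** Section 9.2.4 states: "Exposure-adjusted incidence of TEAEs will also be provided by SOC and PT". The denominator is: "Each individual subject year on study will be derived as the last known date during the study minus the first dose date plus 1"; the day count is then converted to years. It has no cut at IP stop, at IP stop plus 30 days, or at commercial OCALIVA start. Section 9.1 defines exposure to IP, but the rate formula does not use it. Section 9.8 repeats the exposure-adjusted rates by baseline disease stage.

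**Follow-up off drug.** Section 3 says: "Subjects who discontinue IP are expected to be followed through to study closure", subject to Sponsor discretion. Section 8.1.1 plans to tabulate patient time after IP discontinuation and after commercial OCALIVA, by arm. Section 14.1 gives high discontinuation as one reason for stopping the study early.

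**Related analyses.** The on-risk adverse event (ORAE) rates at the end of Section 9.2.4 use a wider window, to 30 days after scheduled visits end, and are cut at commercial OCALIVA. No denominator is stated for them. For MACE, Section 9.3 says: "Subjects without any documentation of events will be censored at the date of last contact".

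**The concern.** A rate needs its events and its person-time to cover the same period. Here the numerator closes 30 days after IP stops, while the denominator runs on to the last known date in the study. A subject followed for years after stopping IP adds those years to the denominator and cannot add a TEAE.

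Two things follow. The absolute rate is too low in any arm with off-IP follow-up beyond 30 days. If one arm has proportionally more of that time, its rates look lower for that reason alone, and any comparison of the two columns misleads. These rates are the TEAE summaries meant to adjust for unequal follow-up, in a trial that the SAP itself describes as having high discontinuation. The disease-stage tables inherit the problem, and there the stopping pattern may differ between subgroups as well as between arms.

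**Working it through.** The SAP states no adverse event rate, person-years or discontinuation rate by arm, so there is no figure of the plan's own to reproduce. The figures below are illustrations under stated assumptions.

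**Step 1. The two windows side by side.**

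| | Starts | Ends |
|---|---|---|
| TEAE numerator (Sections 9, 9.2.1) | first IP dose | IP stop + 30 days |
| TEAE denominator (Section 9.2.4) | first IP dose | last known date during the study |

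The ends coincide only for subjects whose study follow-up ends within 30 days of IP stop.

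**Step 2. Formula.** Let S be years from first dose to last known date and T the years on IP. The 30-day tail is 30/365.25 = 0.082 years. The share of the in-window rate that is retained is

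share = min(S, T + 0.082) / S.

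The apparent rate ratio is the true ratio × share(OCA) / share(placebo). This takes the numerator as events occurring at a constant rate within the window.

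**Step 3. Dilution within an arm.** S = 6 years is assumed, being the approximate minimum follow-up in Section 3; S = 4 is shown for range.

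| Share of time on IP | Retained, S = 6 | Retained, S = 4 |
|---|---|---|
| 80% | 0.81 | 0.82 |
| 60% | 0.61 | 0.62 |
| 50% | 0.51 | 0.52 |
| 40% | 0.41 | 0.42 |
| 30% | 0.31 | 0.32 |

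**Step 4. Effect on the comparison.** S = 6 in both arms, with an assumed true in-window rate of 0.10 per year in both arms.

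| Years on IP, OCA v placebo | Reported rates | Ratio |
|---|---|---|
| 3.6 v 3.6 | 0.061 v 0.061 | 1.00 |
| 3.0 v 4.2 | 0.051 v 0.071 | 0.72 |
| 4.2 v 3.0 | 0.071 v 0.051 | 1.39 |
| 2.4 v 4.2 | 0.041 v 0.071 | 0.58 |
| 4.2 v 2.4 | 0.071 v 0.041 | 1.73 |

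For the second row: (3.0 + 0.082)/6 = 0.514, (4.2 + 0.082)/6 = 0.714, and 0.514/0.714 = 0.72. With a true ratio of 1.5, 3.0 v 4.2 years on IP shows 1.08, and 4.2 v 3.0 shows 2.08.

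**Step 5. Switchers.** Take 3 years on IP, an immediate start of commercial OCALIVA, and 6 years on study. The retained share is 3/3 = 1.00 if subject-years are cut at the switch and 3/6 = 0.50 if they are not. The formula in Section 9.2.4 does not say which applies.

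**Step 6. With matched person-time.** If the denominator ends where the event window ends, the retained share is 1.00 in each arm. A true ratio of 1.00 then shows as 1.00 and 1.5 as 1.50, whatever the stopping pattern.

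**The case against.** The best defence has five parts.

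- **The rates are secondary.** Section 9.2.4 leads with event counts and with numbers and percentages of subjects; the exposure-adjusted rates are additional. Section 9 plans no inferential safety comparison unless otherwise specified, and no adverse event rate ratio is planned. This stands. A reader might infer that the main safety comparison is biased, but the SAP does not give these rates that place, and the crude tables are untouched.
- **Commercial OCALIVA time may already be out.** The Section 9 exclusion can be read as cutting subject-years as well as events, and Section 9 does not define the last known date. This stands as an ambiguity, so one cannot assert that time on commercial drug is in the denominator. It does not rescue the rates: off-IP time in subjects who stop without switching remains.
- **The on-risk rates cover off-drug time.** In part they do, since their window runs through scheduled visits plus 30 days. They are a different measure, though, and do not repair the TEAE rates. A reader might also infer that they share the flaw. That would require the TEAE denominator to carry over, which the SAP does not say; the fair statement is that their denominator is unspecified.
- **MACE is not diluted.** A reader might infer that Section 9.3 repeats the error. If either the Section 9 exclusion or the Section 9.3 censoring rule governs both events and follow-up, nothing is diluted. What the text shows is a conflict between two cut-offs.
- **The sizes are illustrative.** True. Section 9.2.4 also does not say whether the rate's numerator is events or subjects, and the Step 2 relation to the true rate is exact only for events.

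**Conclusion.** The point holds for the TEAE denominator as written. A treatment-emergent numerator is divided by on-study time, and the SAP itself expects follow-up after IP stops. The understatement needs only some subjects followed more than 30 days off IP. The between-arm distortion needs, in addition, a different share of off-IP time in the two arms, which the document neither shows nor rules out.

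Under the assumptions above (6 years on study, constant rates, 2.4 to 4.2 years on IP), equal true rates can show as ratios from 0.58 to 1.73. A reader might infer that the error favours OCA. The SAP does not support a direction: the arm with more off-IP time looks safer, and which arm that is cannot be known from it.

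This should be fixed before reporting. It is not critical, because the affected rates are descriptive, sit beside unaffected counts and percentages, and bear on no hypothesis test. The on-risk denominator and the MACE cut-off are gaps to close at the same time, not demonstrated biases.

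**What to change.** 1. **TEAE rates (Sections 9.2.4 and 9.8).** Define person-time from first dose to the earliest of last IP dose + 30 days, the day before commercial OCALIVA start, death, or last contact.
2. **On-risk rates (end of Section 9.2.4).** State a denominator that matches their window: first dose to the earliest of the end of scheduled visits + 30 days, the day before commercial OCALIVA start, death, or last contact.
3. **MACE (Section 9.3).** State whether the Section 9 exclusion of data after commercial OCALIVA or censoring at last contact governs, and apply the same cut-off to events and follow-up time.

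The cost is SAP wording and derivation code. The SAP already relies on the dates of IP stop, commercial start, visit discontinuation and last contact, so no new data are needed. The reported TEAE rates will rise wherever there is off-IP follow-up beyond 30 days.

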8.1.1. Primary Analyses

The primary efficacy analyses will compare OCA to placebo with respect to the primary efficacy endpoint using the ITT Population. Only adjudicated events will be included in the analysis. The number and percent of subjects censored and with events will be presented. Descriptive statistics will be presented for the time-to-event endpoints.

If a subject experiences more than one event in the composite primary endpoint (all Group 1 – Group 3 events), only the event that occurs first will be included in the analysis. Subjects with no data after randomization will be censored on Day 1 (first day of IP dosing). Subjects who do not experience an event will be censored at the time of their last contact. Last contact is the date of discontinuation from regularly-scheduled study visits for subjects who did not consent to follow-up and the date of discontinuation from contact visits (medical record review / semi-annual phone calls) for patients who consented to follow-up. The total number of patient years observed, patient years and percentage of patient time accrued after discontinuation of IP, and

patient years and percentage of patient time accrued after initiation of commercial OCALIVA will be presented overall and by treatment group.

The 2 treatment groups will be compared using the log rank test stratified by the randomization stratification factors, conducted at the 2-sided alpha level of significance described in [Section 8.6](#). Kaplan-Meier (KM) estimates of the distribution of the time-to-event will be tabulated and graphed by treatment group. The tabulation will include the KM estimate of the 25th, 50th (median), and 75th percentiles and corresponding 2-sided 95% CIs, where the percentiles can be estimated. KM tabulations will present time to event in days; KM graphs will present time to event in months. The hazard ratio and 95% CI will be determined based on a Cox regression model stratified by randomization strata to estimate the magnitude of the effect. The proportionality of hazards will be assessed using Schoenfeld residuals.

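### Exposure-adjusted TEAE rates divide on-treatment events (to last dose + 30 days) by years on study, so the stated person-time does not match the events counted

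*SAP*

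**What the plan says.** **Events counted.** Section 9.2.1 defines a TEAE as an event that is new or worsens after exposure to IP or "within 30 days after the discontinuation of the study treatment". The opening of section 9 uses the same 30-day limit for safety data in general and adds: "Data after a patient begins commercial OCALIVA will be excluded".

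**Person-time.** Section 9.2.4 states: "Exposure-adjusted incidence of TEAEs will also be provided by SOC and PT". The derivation given with it, converted from days to years, is: "Each individual subject year on study will be derived as the last known date during the study minus the first dose date plus 1". Section 9.8 plans the same rates for the disease-stage subgroups and gives no other person-time.

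**On-risk events (ORAEs).** Section 9.2.4 plans a second set of exposure-adjusted rates. Its events run to 30 days after regularly scheduled visits end and are cut at commercial OCALIVA. No separate person-time is given.

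**Follow-up.** Section 3 states: "Subjects who discontinue IP are expected to be followed through to study closure", qualified by the sponsor's discretion. Section 8.1.1 describes contact-only follow-up (record review and semi-annual calls) after scheduled visits stop.

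**The concern.** An incidence rate needs a denominator that covers the time in which an event could enter the numerator, and no more. Here the numerator closes 30 days after the last dose, or earlier if commercial OCALIVA starts. The denominator runs to the last known date on study. A subject who stops IP after two years and is followed for four more adds about two years of countable events and six years of person-time.

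Two things follow. The rate labelled exposure-adjusted is too low whenever subjects remain on study off IP, even if the arms are identical. The comparison between arms also depends on how long each arm stays on study after stopping IP, which is not a property of the drug's safety. These tables feed the descriptive benefit-risk reading. No efficacy inference depends on them.

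**Working it through.** The plan gives no rate and no exposure duration, so it has no figure of its own to reproduce. The check sets the two windows side by side and then illustrates the size.

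**Windows as written**

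| Quantity | Start | End | Cut at commercial OCALIVA |
|---|---|---|---|
| TEAE count (9, 9.2.1) | first dose | IP stop + 30 days | yes |
| ORAE count (9.2.4) | first dose | end of scheduled visits + 30 days | yes |
| Subject-years (9.2.4) | first dose | last known date on study | not stated |

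One denominator serves two numerators that end at different times. It matches neither for a subject who goes on to contact-only follow-up.

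**Formula.** Assume a constant on-treatment event rate λ. Let T be years on IP, F years on study, and w = 30/365.25 = 0.082 years. Then

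stated rate = λ × min(T + w, F) / F.

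The relative error, 1 − min(T + w, F)/F, does not depend on λ.

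**Same durations in both arms** (T and F assumed; λ = 0.20 per year where a rate is shown)

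- F = 6, T = 4: 0.20 × 4.082/6 = 0.136, 32% too low.
- F = 6, T = 3: 0.20 × 3.082/6 = 0.103, 49% too low.
- F = 6, T = 2: 0.20 × 2.082/6 = 0.069, 65% too low.
- F = 4, T = 4, 3, 2: 0%, 23% and 48% too low.

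The ratio between arms stays at 1.00 in all of these.

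**Different durations, true ratio 1.00** (OCA v placebo)

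- Equal F, T = 2 v 3: 2.082/3.082 = 0.68.
- Equal F, T = 1.5 v 3: 1.582/3.082 = 0.51.
- Equal F, T = 3 v 2: 3.082/2.082 = 1.48.

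Different study time alone has the same effect. Take a 3-year TEAE window in both arms, with 5 years on study in one and 4 in the other: (3/4)/(3/5) = 1.25.

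**If the numerator is subjects with a first event.** With λ = 0.10, windows of 3 v 2 years and 5 years on study in both arms, the rates per 100 subject-years are 100 × (1 − e^−0.3)/5 = 5.2 and 100 × (1 − e^−0.2)/5 = 3.6. The ratio is 0.70, so the problem does not depend on counting events rather than subjects.

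**With matched person-time.** When events are counted, replacing F by min(T + w, F) returns λ in each arm, here 0.200 v 0.200, with a ratio of 1.00.

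**The case against.** **Section 9 may already truncate person-time.** The last known date during the study is undefined, and the opening of section 9 limits the safety data. A programmer could apply that limit to the denominator too. This is a fair reading of an ambiguous term, but the sentence defines a year on study and does not mention the limit. If truncation is intended, the text should say so.

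**The ORAE rates cover off-drug time.** They fit on-study person-time better, because their events continue until scheduled visits end. A smaller gap remains for contact-only time and time on commercial OCALIVA. The TEAE rates are not corrected.

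**The reader can see the problem elsewhere.** Section 8.1.1 will report "patient years and percentage of patient time accrued after discontinuation of IP" for each arm, with a similar figure for time on commercial OCALIVA. A marked difference between arms would show there. Section 9.1 also summarises time on IP. Dividing first-event counts by it, with λ = 0.10 and 3 v 2 years, gives 100 × (1 − e^−0.3)/3 = 8.6 and 100 × (1 − e^−0.2)/2 = 9.1, a ratio of 1.05 against a truth of 1.00. This limits the harm but leaves the planned rates wrong. The 9.1 duration also subtracts interruptions and omits the 30 days, so it is not the matching denominator.

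**Off-drug follow-up may be short.** Section 6.4 of the interim SAP reports higher-than-expected discontinuation of the study as well as of treatment, and leaving the study shortens the denominator. This stands, and is why the size is left open.

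**A reader might infer that the adverse events of special interest (AESIs) are mishandled** because their categories get no exposure-adjusted rate. The document does not support calling that an error. Section 9.2.4 plans "The number of events and counts and percentages of unique subjects experiencing a TEAE", with AESIs among the listed categories, and adds severity tables. The stated subject-years are common to all event types, so a category rate can be formed from them. Such rates would be a useful option, not a correction.

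**Conclusion.** The mismatch is in the text. Read as written, 9.2.4 and 9.8 understate TEAE rates for subjects who stop IP and remain on study. They distort the arm ratio only if the on-treatment share of study time differs by arm. The illustrations give 0% to 65% understatement, and ratios of 0.51 to 1.48 for a true 1.00. They rest on assumed durations and a constant event rate.

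A reader might go further and conclude that the plan hides harm from OCA. The documents do not support that. Section 14.1 describes discontinuation as high but gives no split by arm, so the bias could run either way or cancel in the ratio. Severity is low: descriptive safety tables only, with no effect on any efficacy test.

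**What to change.** In 9.2.4, replace the subject-year sentence with person-time that ends with the matching event window:

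- **TEAEs:** first dose to the earliest of last IP dose + 30 days, start of commercial OCALIVA, or last contact.
- **ORAEs:** first dose to the earliest of last regularly scheduled visit + 30 days, start of commercial OCALIVA, or last contact.

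State in 9.8 that the same definitions apply to the subgroup rates.

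The cost is a few lines of SAP text and a changed denominator in tables already planned. Sections 8.1.1 and 9.1 already need the dates involved. The downside is that the rates will not match any earlier output built on on-study years. No new table or test is required.
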